APPENDIX F ABEMACICLIB DOSING INSTRUCTIONS & DRUG DIARY (Cohort 1 Pre-Surgery)

o be completed by study personnel:							
Patient ID #	_ Patient Initials:	Pre-Surgery Cycle Month & Year:	Abemaciclib Dose:	_mg, two times a day.			
	TAKE	pill(s) in the morning and	_ pill(s) in the evening.				

Abemaciclib Description:

• Your study drug (Abemaciclib) is supplied as 50 mg mixture beige tablet.

Abemaciclib Instructions - When and How:

- Take study drug (Abemaciclib) twice a day, once in the morning and once in the evening.
- Take the drugs at approximately the same time each morning and evening, so that you are taking the drugs 12 hours apart. Morning and evening doses should be taken as close to a 7AM & 7PM schedule as possible (7 in the morning, 7 at night, 7 the next morning, and so on).
- Take the pill(s) with a glass of water and swallow them whole; do not chew them or crush them. Abemaciclib can be taken with or without food.
- Do not skip any doses.
- If you forget to take your pills in the morning you can take your missed dose up to 6 hours after your normally scheduled time. If it has been more than 6 hours, skip the dose and take the next scheduled dose at the usual time in the evening (one dose only). Please call your study nurse or doctor to discuss missed doses.
- If you forget to take your pills in the evening, you can take your missed dose up to 6 hours after your normally scheduled time. If it has been more than 6 hours from the missed dose (i.e., less than 6 hours to your next scheduled dose), skip the dose and take the next scheduled dose at the next usual time (one dose only). Please call your study nurse or doctor to discuss missed doses.
- If you vomit your pills, write this down in your pill diary. Do not take a replacement dose. Take the next scheduled dose as usual (one dose only). Please call your study nurse or doctor to discuss vomited doses.
- On the day of surgery, you will be asked to take your morning dose at the hospital; therefore, please bring your pills with you. Do not take any further doses after surgery. Return any remaining pills to the study team.

Additional Instructions:

- You must avoid eating or drinking any foods with Seville oranges (like marmalade), grapefruit or foods or drink with grapefruit, and any exotic fruits during the entire treatment period.
- You should drink 8 to 10 glasses of clear liquids a day for the entire treatment period.
- Keep your study drug in the original container(s) at room temperature. Keep study drug away from children, persons cannot read the label, and pets.
- Do not throw away empty bottles, and do not throw the study drug in the trash or flush into the toilet.
- Bring this diary, all pill bottles, and any unused pills to each clinic visit. Your Treatment Team will collect your diary, all pill bottles and any unused study drug, and you will be given a new pill diary at that time.
- Contact your study doctor or nurse if you are having any new or worsening side effects. Contact your study doctor or nurse as soon as possible if you are experiencing diarrhea.
- Do not begin any new medication, over-the-counter drug, or herbal preparation without first checking with your study doctor or nurse to determine if it is acceptable to take while on this study.

Day 1	Day 2	Day 3	Day 4	Day 5	Day 6	Day 7
Date:	Date:	Date:	Date:	Date:	Date:	Date:
A.M. DOSE	A.M. DOSE	A.M. DOSE	A.M. DOSE	A.M. DOSE	A.M. DOSE	A.M. DOSE
No. of pills:	No. of pills:	No. of pills:	No. of pills:	No. of pills:	No. of pills:	No. of pills:
Time:	Time:	Time:	Time:	Time:	_ Time:	Time:
P.M. DOSE	P.M. DOSE	P.M. DOSE	P.M. DOSE	P.M. DOSE	P.M. DOSE	P.M. DOSE
No. of pills:	No. of pills:	No. of pills:	No. of pills:	No. of pills:	No. of pills:	No. of pills:
Гіте:	Time:	Time:	Time:	Time:	Time:	Time:
Initials	 Initials		 Initials	Initials	 Initials	 Initials
Day 8	Day 9	Day 10	Day 11	Day 12	Day 13	Day 14
Date:	Date:	Date:	Date:	Date:	Date:	Date:
A.M. DOSE	A.M. DOSE	A.M. DOSE	A.M. DOSE	A.M. DOSE	A.M. DOSE	A.M. DOSE
No. of pills:	No. of pills:	No. of pills:	No. of pills:	No. of pills:	_ No. of pills:	No. of pills:
Гіте:		Time:	Time:	Time:	_ Time:	Time:
P.M. DOSE	P.M. DOSE	P.M. DOSE	P.M.DOSE	P.M. DOSE	P.M. DOSE	P.M. DOSE
No. of pills:	_ No. of pills:	No. of pills:	No. of pills:	No. of pills:	No. of pills:	No. of pills:
Time:	_ Time:	Time:	Time:	Time:	Time:	Time:
Initials						 Initials
Please stop takii	ng abemaciclib after on-stud	ly surgery until you are ex	valuated by the study tear	m. All unused study med	lication should be returne	ed to the study team.
	Participant/Guard	lian Signature:		Date:		
	To be completed by	y study personnel: # o	f 50 mg Bottles Returned:	# of 50 m	ng Pills Returned:	
	Compare with drug diary ent	ries made by participant or	guardian. If discrepancy	(in the # of bottles or the	# of pills returned), pleas	e reconcile:
	Study Perso	nnel Signature:		Date:		

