In other preclinical data we studied effects of abemaciclib (LY2835219) on a panel of GBM patient derived cell line models (PDCLs) which faithfully recapitulate the biology and genotype of GBM patients along with their diversity. This work shows that the initial biomarker hypothesis that CDKN2A homozygous deletion (or greater than 1 copy loss) is associated with increased sensitivity to the drug and CDK4 amplification is associated with relative resistance.

Cerebrospinal fluid (CSF) samples were collected from a limited number of patients with brain metastases in Study JPBA on Day 15 of Cycle 1 after repeated Q12H dosing. In general, abemaciclib concentrations in CSF were consistent with unbound plasma concentrations. The metabolite concentrations were lower than abemaciclib concentrations and in some patients below the lower limit of quantitation (1 ng/mL).

Dosing and Method of Administration

[figure not shown]

Figure 1. GBM PDCLs treated with LY2835219 (Abemaciclib) show differential response based on genotype with CDKN2A deleted lines (>1 copy loss) being more sensitive than lines with intact CDKN2A.. ([name], unpublished)

Abemaciclib has been administered orally on Days 1 through 28 of a 28-day cycle. In Study JPBA, the MTD for humans when administered as a single agent is 200 mg Q12H. During the tumor-specific expansion phases of JPBA, patients initially received abemaciclib at the MTD of 200 mg Q12 hours. A preliminary interim safety review with data from 56 patients indicated that 29 patients experienced diarrhea possibly related to study drug: 17 Grade 1 (30%), 9 Grade 2 (16%), 3 Grade 3 (5%), none Grade 4 (0%), and none Grade 5 (0%). Based on the frequency of Grade 1/2 diarrhea and the observation of clinical activity at doses below the MTD, the initial starting dose was changed to 150 mg every 12 hours to gain additional PK data and clinical experience around safety/tolerability. Based on this further clinical experience (demonstrating that the diarrhea experienced by patients is manageable with standard anti-diarrheal agents such as loperamide) the study was further amended to again allow starting doses of 200 mg Q12H. Therefore, for safety, the starting dose of abemaciclib in this phase 2 study in recurrent GBM will be 150 mg Q12H. Abemaciclib may be escalated at the start of Cycle 2 to 200 mg Q12H if the investigator determines that it is in the best interest of the patient.

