Dosages for pediatric and geriatric populations are not known at this time. There is no information for dosage adjustments in patients with renal insufficiency, hepatic insufficiency, or

concomitant disease, or who are undergoing dialysis.

Safety and Efficacy

Validated safety data for 352 patients treated with abemaciclib in Studies JPBA, JPBB, JPBC, JPBH, JPBJ, and JPBN are available. Cumulatively, the most common TEAEs ($\geq 10\%$) possibly related to study drug for patients receiving abemaciclib either as a single agent, with endocrine therapy, or with chemotherapy, are diarrhea (64.2%), nausea (44.3%), fatigue (39.8%), neutropenia (27.0%), vomiting (24.1%), thrombocytopenia (21.3%), leukopenia (21.0%), anemia (17.6%), decreased appetite (17.6%), and blood creatinine increased (14.5%).

The majority of deaths reported for patients in the studies with available safety data were due to study disease.

As of 14 October 2014, 31 patients in Studies JPBA, JPBB, JPBC, JPBE, JPBH, JPBJ, and JPBN experienced 43 SAEs that were reported as possibly related to study drug. SAEs that were possibly related to study drug and experienced by more than 1 patient included diarrhea (5 patients), dehydration (4 patients), neutropenia and pneumonia (3 patients each), and anemia, confusional state, nausea, pyrexia, and sepsis (2 patients each).

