As the study continued, the nonsurgical cohort (Cohort 2) completed accrual while the surgical cohort (Cohort 1) remained open. Outcomes data were reviewed in the nonsurgical cohort (Cohort 2) demonstrating limited benefit from abemaciclib monotherapy with a PFS6 rate of 9.37% [95% CI, 2.4%, 22.27%], median PFS 55 days [95% CI, 49, 56], and median OS 384 days [95% CI, 228, 488]. Nonetheless, a surgical cohort still provides valuable information to understanding why abemaciclib has limited activity in recurrent GBM patients and whether it helps enhance the antitumor immune response (Goel et al., 2017). Therefore, the study was amended further to convert the remaining slots in the surgical cohort (Cohort 1) into a Phase 0 study. The study design remains the same (pretreatment with abemaciclib followed by surgery with correlative studies) except that participants will come off study treatment after surgery and pursue standard cancer treatments as per the treating physician's discretion. The purpose of this phase 0 study is not to treat the tumor but to determine tumor tissue PK and PD. This phase 0 study does not replace routine cancer treatment.

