Thrombocytopenia - Grade 4 (PLT < 25 x 10 ⁹ /L)	Interrupt until resolved to ≤ grade 2, then resume ABEMACICLIB at one lower dose level
Patient requires administration of a blood cell growth factor	Suspend abemaciclib dose for at least 48 hours after the last dose of blood cell growth factor and until toxicity resolves to ≤Grade 2.
	Resume abemaciclib at next lower dose unless the dose was already reduced for the toxicity that led to the use of the growth factor.
	•

Gastrointestinal Disorders

Guidelines for Diarrhea Management

Clinical trial data indicates the majority of patients who receive abemaciclib will develop diarrhea. Our experience indicates early identification and intervention for the management of diarrhea has been helpful to patients.

At enrollment, patients should receive instructions on the prompt management of diarrhea. In the event of diarrhea, supportive care measures should be initiated as early as possible. These include the following:

- At the first sign of loose stools, the patient should initiate antidiarrheal therapy (e.g. loperamide) and notify the investigator for further instructions and appropriate follow up.
- Patients should also be encouraged to drink fluids (e.g., 8 to 10 glasses of clear liquids per day).
- Site personnel should assess response within 24 hours.

Diarrhea - Grade 2 (4-6 stools/day > pretx)	If diarrhea can be controlled with optimal anti-diarrheal treatment within 24 hours to either baseline or grade 1, continue ABEMACICLIB. If not, interrupt treatment until resolved to \leq grade 1, then resume ABEMACICLIB at the current dose (treating investigators may reduce by 1 dose level at their own discretion for first occurrence). If diarrhea persists or returns as \geq grade 2, then interrupt treatment until resolved to \leq grade 1, then resume ABEMACICLIB at one lower dose level.
Diarrhea - Grade 3 (7-9 stools/day > pretx) - Grade 4 (≥ 10 stools/day > pretx) (requires hospitalization)	If diarrhea can be controlled with optimal anti-diarrheal treatment within 24 hours to either baseline or grade 1, continue ABEMACICLIB. If not, for diarrhea \geq Grade 3 or requires hospitalization, interrupt treatment until resolved to \leq grade 1, then resume ABEMACICLIB at one lower dose level.

Respiratory, Thoracic, and Mediastinal Disorders

General Guidance for Interstitial lung disease (ILD)/Pneumonitis events

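### Both patient diaries put checking with the team before any over-the-counter drug, while Table 6.3 wants the patient to start an antidiarrheal at the first loose stool

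*Combined protocol and SAP*

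**What the plan says.** Table 6.3, in section 6.2, contains a guideline for managing diarrhea. It sets a general aim, "In the event of diarrhea, supportive care measures should be initiated as early as possible", and then assigns the first step to the patient: "At the first sign of loose stools, the patient should initiate antidiarrheal therapy (e.g. loperamide) and notify the investigator". It also requires preparation beforehand: "At enrollment, patients should receive instructions on the prompt management of diarrhea".

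Appendix F is the diary for the pre-surgery period of Cohort 1. Under its additional instructions it says "Do not begin any new medication, over-the-counter drug, or herbal preparation without first checking with your study doctor or nurse", the purpose being to establish whether the product is acceptable on study. Its only line on what to do about diarrhea is "Contact your study doctor or nurse as soon as possible if you are experiencing diarrhea". Appendix E, the diary for Cohort 2 and for post-surgery Cohort 1, has the same two lines. Neither diary names an antidiarrheal, makes an exception for one, or points to other diarrhea instructions.

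The opening of section 5.4 sets the same general rule as the diaries: products bought without prescription need consultation with the investigator beforehand. The exceptions listed after it do not mention antidiarrheals.

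**The concern.** The two instructions give the same patient a different order of action. Table 6.3 says treat and notify; the diaries say check, then treat. Section 5.1 refers to the diary for dosing instructions, so the diary is a sheet the patient has at hand when loose stools begin.

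The protocol relies on early treatment of this toxicity. In section 2.2, further experience that "the diarrhea experienced by patients is manageable with standard anti-diarrheal agents such as loperamide" is part of the account of how the starting dose was settled in Study JPBA. Table 6.3 also ties dosing to it: at Grade 2 and above, abemaciclib continues if optimal antidiarrheal treatment brings the event to baseline or Grade 1 within 24 hours, and is otherwise interrupted. A patient who waits for permission could therefore have symptoms for longer than the protocol intends. This is a matter of patient safety. It does not touch the sample size, the error rates or the primary endpoint.

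**Working it through.** **Text comparison.** The claim rests on wording, so the instructions are set side by side.

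| Place | Over-the-counter drugs | Diarrhea |
|---|---|---|
| Table 6.3 | – | Patient starts an antidiarrheal at the first loose stool and notifies the investigator |
| Appendix F | None to be begun before checking | Contact the team promptly |
| Appendix E | Same as Appendix F | Same as Appendix F |
| Section 5.4, opening | None without prior consultation | No exception stated |

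Loperamide or a similar agent bought by the patient falls under the diary's over-the-counter line. Read literally, that line holds the drug back until someone has answered. Table 6.3 does not. It asks site staff to assess response within 24 hours, which presumes that treatment has already begun. The conflict is in the order of steps, and nothing in the diary says which instruction prevails.

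**How common the toxicity is.** Both inputs are in section 2.2, and intervals are exact (Clopper-Pearson).

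- Pooled safety data: 0.642 × 352 = 226 patients with possibly related diarrhea; 95% CI 59.0% to 69.2%. The pool includes combinations with endocrine therapy and chemotherapy.
- JPBA interim review: 17 Grade 1 + 9 Grade 2 + 3 Grade 3 = 29 of 56, or 51.8%; 95% CI 38.0% to 65.3%. None was Grade 4 or 5. The text implies 200 mg every 12 hours for these patients but does not say so for all 56.

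**Who is still exposed.** Section 2.4 says the study was amended to "convert the remaining slots in the surgical cohort (Cohort 1) into a Phase 0 study", but not how many slots remain. As an assumption, take 5 new participants: 5 × 0.518 = 2.6 and 5 × 0.642 = 3.2 with diarrhea. These are upper-range values, because neither source is limited to 10–14 days of dosing and the starting dose here is 150 mg.

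The documents do not show how many patients would delay treatment, or for how long, so no rate of delay or harm can be derived.

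**The case against.** The strongest reply is that the three texts can be followed together. The diary does not forbid an antidiarrheal; it forbids starting one unchecked. Table 6.3 requires diarrhea instructions at enrollment, so a patient told then to use loperamide has already checked. On this reading only a cross-reference is missing. This stands in part: the enrollment instructions may well be the prior check. It does not settle the matter, because neither diary refers to them and section 5.4 gives no exception. A patient taught one thing at enrollment and holding a sheet that says another has no written way to tell which applies.

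Other points also deserve weight:

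- The consent pages are not in this copy and the enrollment instructions are not shown, so a separate diarrhea sheet may exist. The finding is established for the diaries and section 5.4 only.
- Both diaries advise 8 to 10 glasses of clear liquids a day, which matches a measure in Table 6.3. They give it as a daily habit, though, not as a response to diarrhea.
- No text says that Table 6.3 outranks section 5.4, and section 5.4 uses the stronger verb (must, against should). Giving Table 6.3 precedence is a judgment, based on its being the specific guidance for this event.
- Most JPBA events were low grade: 26 of 29 were Grade 1 or 2. The reach is also narrow, since Cohort 2 has finished accrual and new Cohort 1 participants stop the drug at surgery.

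These points limit the size of the problem but do not remove the conflict in the written instructions.

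**Conclusion.** The concern holds. Followed literally, both diaries and section 5.4 put checking before treatment of a toxicity that the protocol wants treated at the first loose stool. The toxicity is common: 64.2% of 352 patients in the pooled data and 52% of 56 in the JPBA review. Those figures describe diarrhea, not harm from the wording, which the documents do not allow anyone to estimate. The projection of 2.6 to 3.2 cases per 5 new participants rests on an assumed number of slots and on rates from different dosing conditions.

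The change should be made, because it concerns a safety instruction for the drug's most common toxicity and costs very little. Confidence is medium, mainly because the enrollment instructions are not visible and may already close much of the gap in practice.

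**What to change.** Treat the Table 6.3 diarrhea guideline as governing, and align the other texts with it.

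1. In Appendix F and Appendix E, add to the over-the-counter line: *Exception: at the first loose stool, start the antidiarrheal (e.g. loperamide) as you were instructed at enrollment, and contact your study doctor or nurse as soon as possible.*
2. At the opening of section 5.4, add: *Antidiarrheals started per the Table 6.3 diarrhea guideline, as instructed at enrollment, are covered by this consultation.*
3. Give the revised Appendix F to new Cohort 1 participants. Give the revised Appendix E to any participant still on drug, which section 5.2 allows for those who started post-surgical dosing before the conversion and are benefitting.

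The exception covers only what was taught at enrollment and keeps the duty to notify, so it does not loosen the rule for other products. The cost is one sentence in each diary and one cross-reference at the next amendment, plus reissue of the diary page. It needs no extra visits, data fields or patients.

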APPENDIX G MRI ACQUISITION PROTOCOL

Brain MRI will be acquired at baseline and every 8 weeks after treatment initiation as detailed in Section 10 Study Calendar. All MRI exams will be performed based on standardized parameters recommended by the Jumpstarting Brain Tumor Drug Development Coalition Imaging Standardization Steering Committee (Ellingson et al. Neuro Oncol. 2015 Sep;17(9):1188-98). The following sequences are included: (i) parameter-matched precontrast and postcontrast inversion recovery-prepared, isotropic 3D T1-weighted gradient-recalled echo; (ii) axial 2D T2weighted turbo spin-echo acquired after contrast injection and before postcontrast 3D T1weighted images to control timing of images after contrast administration; (iii) precontrast, axial 2D T2-weighted fluid-attenuated inversion recovery; and (iv) precontrast, axial 2D, 3-directional diffusion-weighted images. The T2-weighted sequence should be performed following contrast injection, before acquisition of T1-weighted post-contrast sequences. The protocol can also include additional advanced imaging sequences such as perfusion weighted imaging (PWI) and susceptibility weighted imaging (SWI). Detailed parameters are listed in Table below. When possible, MRI exams should be done using the same MRI scanner for each subject. If this is not achievable, patients should at the very least be scanned on MRI scanners with the same field strength (1.5T or 3T). The chemical composition and dose of gadolinium contrast agents should also be the same for each patient during trial and should be explicitly documented on the MR system during acquisition or labeled in the DICOM header.

Table: MRI Protocol

- 1. Localizer
- 2. Axial 3D T1w (IR-GRE)¹
- 3. Ax 2D FLAIR²
- 4. Ax 2D SS-EPI DWI³
- 5. Ax GRE or Ax SWI
- 6. Contrast Injection
- 7. Ax EPI Perfusion
- 8. Ax 2D SE T2w⁴
- 9. Axial 2D SE T1w
- 10. Axial 3D T1w (IR-GRE)1

Sequence TSEc SS-EPIg Contrast Injectiona TSEc IR-GREe,f

Plane Axial Axial Axial Sagittal/axial

Mode 2D 2D 2D 3D

- 1. TR [ms] 2100, TI [ms] 1100, Flip angle 10°−15°, Frequency ≥172, Phase ≥172, NEX ≥1, FOV 256 mm, Slice thickness ≤1.5 mm. Gap/spacing 0, Parallel imaging up to 2x
- 2. TR [ms] >6000, TE [ms], 100-140, TI [ms] 2000-2500, Flip angle $90^{\circ}/\ge 160^{\circ}$, Frequency ≥ 256 , Phase ≥ 256 , NEX ≥ 1 , FOV 240 mm, Slice thickness ≤ 4 mm, Gap/spacing 0, Parallel imaging up to 2x
- 3. TR [ms] >5000, TE [ms], Flip angle 90°/180°, Frequency ≥128, Phase ≥128, NEX ≥1, FOV 240 mm, Slice thickness ≤4 mm, Gap/spacing 0, Parallel imaging up to 2x, b = 0, 500, 1000 s/mm2 ≥3 directions
- 4. TR [ms] >2500, TE [ms], 80–120, Flip angle 90°/≥160°, Frequency ≥256, Phase ≥256, NEX ≥1, FOV 240 mm, Slice thickness ≤4 mm, Gap/spacing 0, Parallel imaging up to 2x. Post-contrast sequence (10) should be obtained within 8 minutes from time of contrast injection.
